19.2 Table and figure plan

14.1 Demographic data

Table 14.1.1 Number of randomized patients per center

Table 14.1.2 Disposition of patients

Table 14.1.3 Analysis datasets

Table 14.1.4 Descriptive statistics of demographics variables

Table 14.1.5 Details on leukemia diagnosis

Table 14.1.6 Details of prior therapy

Table 14.1.7 Current symptoms and / or residual toxicities from prior therapies

Table 14.1.8 Summary of other medical history

Table 14.1.9 Results of HIV and pregnancy tests

Table 14.1.10 Summary of concomitant medication

14.2 Efficacy data

Figure 14.2.1 Kaplan-Meier curves for Overall survival (ITT)

Figure 14.2.2 Kaplan-Meier curves for Recurrence-free survival (ITT)

Figure 14.2.3 Kaplan-Meier curves for Event-free survival (ITT)

Figure 14.2.4 Kaplan-Meier curves for Overall survival (censoring at time of SCT) (ITT)

Figure 14.2.5 Kaplan-Meier curves for Recurrence-free survival (censoring at time of SCT) (ITT)

Figure 14.2.6 Kaplan-Meier curves for Event-free survival (censoring at time of SCT) (ITT)

14.2.1 Analysis of treatment Response

Table 14.2.1.1 Frequency table for best treatment response overall and by dosing schedule (ITT)

Table 14.2.1.2 Frequency table for best treatment response overall and by dosing schedule (PP)

Table 14.2.1.3 Response rates (CR/CRi) overall and by dosing schedule (ITT)

Table 14.2.1.4 Response rates (CR/CRi) overall and by dosing schedule (PP)

14.2.2 Secondary efficacy analysis

Table 14.2.2.1 Rate of partial remission overall and by dosing schedule (ITT)

Table 14.2.2.2 Rate of partial remission overall and by dosing schedule (PP)

Table 14.2.2.3 Percentage of patients being transplanted after induction therapy (ITT)

Table 14.2.2.4 Percentage of patients being transplanted after induction therapy (PP)

Table 14.2.2.5 Early death rate (ITT)

Table 14.2.2.6 Early death rate (PP)

Table 14.2.2.7 Summary statistics for overall survival endpoint (ITT)

Table 14.2.2.8 Summary statistics for overall survival endpoint (PP)

Table 14.2.2.9 Summary statistics for recurrence-free survival endpoint (ITT)

Table 14.2.2.10 Summary statistics for recurrence-free survival endpoint (PP)

Table 14.2.2.11 Summary statistics for event-free survival endpoint (ITT)

Table 14.2.2.12 Summary statistics for event-free survival endpoint (PP)

14.2.3 Additional efficacy analyses

Table 14.2.3.1 Summary statistics for overall survival endpoint, censoring at time of SCT (ITT)

Table 14.2.3.2 Summary statistics for recurrence-free survival endpoint, censoring at time of SCT (ITT)

Table 14.2.3.3 Summary statistics for event-free survival endpoint, censoring at time of SCT (ITT)

14.2.4 Subgroup analyses

Table 14.2.4.1 Response rates (CR/CRi) by primary vs. secondary AML

Table 14.2.4.2 Response rates (CR/CRi) by length of remission

Table 14.2.4.3 Response rates (CR/CRi) by prior SCT

Table 14.2.4.4 Response rates (CR/CRi) by karyotypic risk group

Table 14.2.4.5 Response rates (CR/CRi) by mutation (FLT3 vs NPM1)

14.3 Safety data

14.3.1 Extent of exposure

Table 14.3.1.1 Extent of exposure

14.3.2 Adverse events

Table 14.3.2.1 Summary of all adverse events

Table 14.3.2.2 Number of patients with adverse events, by clinical/laboratory event category and CTC term

Table 14.3.2.3 Number of patients with adverse events of grades 3 and 4(5), by decreasing frequency of CTC term

Table 14.3.2.4 Number of patients with adverse events, by clinical/laboratory event category, CTC term and maximum severity

Table 14.3.2.5 Number of patients with related adverse events by clinical/laboratory event category and CTC term

Table 14.3.2.6 Number of patients with non-related adverse events by clinical/laboratory event category and CTC term

Table 14.3.2.7 Adverse events leading to treatment discontinuation

Table 14.3.2.8 Number of Serious adverse events

Table 14.3.2.9 Number and reasons for death

14.3.3 Laboratory safety variables

- Table 14.3.3.1 Review of safety laboratory variables, hematology
- Table 14.3.3.2 Abnormal/Normal safety laboratory variables; hematology
- Table 14.3.3.3 Review of safety laboratory variables, clinical chemistry
- Table 14.3.3.4 Abnormal/Normal safety laboratory variables; clinical chemistry
- Table 14.3.3.5 Review of safety laboratory variables, urine analysis
- Table 14.3.3.6 Abnormal/Normal safety laboratory variables; urine analysis
- Table 14.3.3.7 Review of safety laboratory variables, coagulation tests
- Table 14.3.3.8 Abnormal/Normal safety laboratory variables; coagulation tests

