2.2 Secondary Objectives

Secondary objectives of the study are:

- To determine the efficacy of Selinexor in combination with standard chemotherapy in patients with relapsed/ refractory AML by:
 - Rate of partial remissions
 - Percentage of patients being transplanted after induction therapy
 - Early death rate
 - Overall survival (OS)
 - Event-free survival (Events are defined as Death, not achieving a CR or CRi, Relapse after CR or CRi)
- To evaluate overall safety and tolerability of Selinexor characterized by type, frequency, severity (graded using the National Cancer Institute Common Terminology Criteria for Adverse Events [NCI CTCAE] Version 4.03), timing and relatedness of adverse events (AEs) and laboratory abnormalities observed during the treatment within this study

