7.5 Laboratory Test Abnormalities

Laboratory test results will be recorded on the laboratory results pages of the CRF. In the event of unexplained abnormal laboratory test values, the tests should be repeated immediately and followed up until they have returned to the normal range and/or an adequate explanation of the abnormality is found. Laboratory test value abnormalities as such should not be reported on the AE page of the CRF as adverse events unless they are judged clinically significant by the investigator.

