13.1 Adverse events

All adverse events occurring during the course of the trial and for up to 30 days after the last dose of study medication will be captured, documented and reported. The number of patients developing adverse experiences will be tabulated using [NCI CTCAE] Version 4.03. The CTC v4.03 will be the basis for grading the laboratory changes. Additionally, the subset of adverse experiences considered treatment-related will be summarized. Listings of adverse experiences leading to treatment discontinuation will be provided.

Clinical adverse events and laboratory adverse events will be reported in separate tables. The adverse events will be reported as a whole and additionally based on the severity grading (separate table for grade 3-5 AEs).

Adverse events classified as serious adverse events (SAEs) will be listed separately. Deaths together with the reason for death and the possible relation to study treatment will be summarized.

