13.2 Laboratory safety variables

Descriptive statistics of laboratory safety variables (hematology, clinical chemistry, urine analysis, coagulation tests) will be computed, together with the changes from baseline values. The changes from baseline will be analyzed by ANOVA method if feasible.

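### No planned laboratory table grades measured values by CTCAE; graded laboratory rates come only from AE-page entries that depend on the investigator's view of clinical significance

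*SAP*

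**What the plan says.** Protocol 2.2 sets a secondary objective of describing safety by type, frequency, CTCAE-graded severity, "timing and relatedness of adverse events (AEs) and laboratory abnormalities observed during the treatment within this study". SAP 13.1, in a sentence that also stands in protocol 8.4.4, states: "The CTC v4.03 will be the basis for grading the laboratory changes".

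For measured laboratory values, SAP 13.2 says that descriptive statistics "will be computed, together with the changes from baseline values. The changes from baseline will be analyzed by ANOVA method if feasible". The table plan in SAP 19.2 lists eight laboratory tables, 14.3.3.1 to 14.3.3.8. For each of hematology, chemistry, urine and coagulation there is one Review table and one Abnormal/Normal table; the second table in the list is "Abnormal/Normal safety laboratory variables; hematology".

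For adverse events, SAP 13.1 says "Clinical adverse events and laboratory adverse events will be reported in separate tables" and adds a separate table for grades 3 to 5. Table 14.3.2.4 is "Number of patients with adverse events, by clinical/laboratory event category, CTC term and maximum severity", and Table 14.3.2.3 covers grades 3 and 4(5).

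What reaches those tables is governed by protocol 7.5. All laboratory results go on the CRF laboratory pages, but abnormal results taken alone "should not be reported on the AE page of the CRF as adverse events unless they are judged clinically significant by the investigator".

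**The concern.** Severity grading of laboratory abnormalities is called for, yet the tables built from measured values carry no grade. The tables that do carry a grade are built from entries filtered by a judgement that the documents do not define.

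The grades matter because Table 3 in protocol 6.3.1 is organised around them for sodium, bilirubin, AST/ALT, platelets and neutrophils. SAP 8 also asks for all study data by dosing schedule (40 mg/m² against flat 60 mg). A difference in laboratory toxicity between schedules would be read largely from the graded AE tables, and so from discretionary entries at 6-8 sites.

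**Working it through.** The plan gives no figure on this point, so the check sets the texts side by side.

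1. **What is called for.** Protocol 2.2 names laboratory abnormalities alongside adverse events, both under CTCAE-graded severity. SAP 13.1 and protocol 8.4.4 make CTCAE v4.03 the basis for grading laboratory changes.

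2. **What is planned from measured values.** SAP 13.2 gives descriptive statistics, change from baseline, and ANOVA if feasible. Table count: 4 Review + 4 Abnormal/Normal = 8. Titles naming a grade, a worst grade or a shift: 0 of 8.

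3. **What is planned by grade.** Of the AE tables, 14.3.2.3 and 14.3.2.4 name grade or severity in the title, and 14.3.2.4 names a laboratory category. Both count adverse events.

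4. **What feeds the graded tables.** Under protocol 7.5, only abnormalities judged clinically significant. The documents do not define that term.

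5. **Why judgements could differ.** Protocol 6.5.7 reports Grade 3 hyponatremia in 283 selinexor-treated patients (24%), with no symptomatic case and all quickly corrected. Protocol 6.3.4 says electrolyte abnormalities reversible with standard measures do not require selinexor to be held. One investigator could reasonably enter such a value as an adverse event and another leave it off. Cytopenia expected after induction chemotherapy raises the same question.

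6. **What the binary table loses.** On the sodium bands in protocol Table 3, a value between 130 and the lower limit of normal is Grade 1 and a value under 120 is Grade 4. Both are simply abnormal in an Abnormal/Normal table.

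7. **Scale, as illustration only.** Assume the 24% applied to this trial: 0.24 × 40 = 9.6, about 10 patients with Grade 3 hyponatremia. If a share c of them reached the AE page, the graded table would show 9.6 × c. The documents give no value for c. With c anywhere from 0 to 1, the count lies between 0 and 9.6, which is a bound and not an estimate.

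8. **What measured values could supply.** Protocol Table 2 schedules hematology twice weekly in induction, so a worst grade is well supported. Clinical chemistry in induction is scheduled only at end of cycle, so a derived worst grade can miss a peak within the cycle.

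**The case against.** The strongest reply is that the grading sentence sits inside the adverse-event paragraph in both documents. Read there, it says how laboratory adverse events are graded, and Table 14.3.2.4 delivers that. This is a fair reading of the sentence alone. It does not settle the matter, because protocol 2.2 lists laboratory abnormalities separately from adverse events.

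A second reply is that discretion under 7.5 is narrower than it looks. The synopsis requires toxicity grading twice weekly during treatment, Table 2 has a CTCAE toxicity row, and every dose modification or delay must be documented with its reason. An event that forces an interruption is unlikely to be called insignificant. This stands in part. It does less for toxicity judged unrelated to selinexor, which Table 3 does not cover, or for the electrolyte changes exempted in 6.3.4.

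A third reply is that extremes are not hidden. SAP 8 gives minimum and maximum by visit, and SAP 17 plans patient listings. This is correct, but a minimum shows one value and not how many patients reached a grade.

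A reader might infer that the SAP contains no graded laboratory output, or that Grade 3-4 laboratory rates cannot be reported at all. Neither holds: Tables 14.3.2.3 and 14.3.2.4 are graded, and the values needed for more are on the CRF. A reader might also infer that the Abnormal/Normal hematology table can show almost no change because nearly every patient starts abnormal. The documents give no baseline rate, and only table titles are available.

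**Conclusion.** The point holds as a gap in the table plan. CTCAE grading of laboratory abnormalities is called for, no table in 14.3.3 derives a grade from measured values, and the graded tables that exist capture only what investigators judged clinically significant. Grade 3-4 laboratory rates from the planned tables may be under-counted and may differ by site. How far cannot be computed from the documents.

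This rests on two assumptions: that the laboratory AE tables are fed only by AE-page entries, and that the Review and Abnormal/Normal tables contain no grading beyond what their titles say.

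Value-derived grades should not be presented as unbiased. They would be sound mainly for hematology and incomplete for chemistry in induction. Nor would they make the comparison of dosing schedules more than descriptive: it is non-randomized, with 25 and 15 patients planned.

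**What to change.** In SAP 13.2 and 14.3.3, add two sets of tables derived by program from the CRF laboratory values for all dosed patients, overall and by dosing schedule:

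- worst post-baseline CTCAE v4.03 grade, with the Grade 3-4 proportion and its 95% CI (the Wilson method of SAP 12.1 would serve);
- shift from baseline grade to worst post-baseline grade.

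Cover hemoglobin, neutrophils and platelets, and for chemistry sodium, potassium, creatinine, bilirubin, ALT and AST. Show patients without a post-baseline value in their own row, so that the denominator stays at all dosed patients. Footnote the chemistry tables to say that induction sampling is scheduled only at end of cycle and within-cycle peaks may be missed. Label the laboratory entries in the adverse event tables as investigator-reported.

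The existing tables and the ANOVA can stay; removing them is not needed for this point.

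**Cost.** SAP wording and some programming, with no new data collection, provided the site normal ranges are held with the values (an assumption; the liver bands in protocol Table 3 are multiples of the upper limit of normal). The April 2018 addendum shows that tables can be re-run by addendum. The downside is two sets of rates that may disagree: value-derived rates are likely to be higher than AE-page rates for hematology and possibly lower for chemistry. The report should explain why.

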14.3.4 Other safety variables

- Table 14.3.4.1 Descriptive statistics of vital signs by visit
- Table 14.3.4.2 Change from baseline in vital signs
- Table 14.3.4.3 Descriptive statistics of body weight by visit
- Table 14.3.4.4 Change from baseline in body weight
- Table 14.3.4.5 Review of physical examination
- Table 14.3.4.6 Frequency tables for ECG by visit
- Table 14.3.4.7 Frequency tables for ECOG by visit

EudraCT No.: 2014-000526-37

Study Code: SAIL

Study Title: An Investigator-Initiated Study To Evaluate Ara-C and Idarubicin in Combination with the Selective Inhibitor Of Nuclear Export (SINE) Selinexor (KPT-330) in Patients with Relapsed Or Refractory AML

Addendum to Statistical Analysis Plan dated 2017Aug25

Addendum to Statistical Analysis Plan dated 2017Aug25

Date and version of the addendum: Version 1, 2018Apr04

Sponsor: GSO Global Clinical Research B.V.

Principal Investigator: [name]. [name], Hamburg

The addendum to the Statistical Analysis Plan was approved by:

10 Apr 2018

[figure not shown]
Date

Signature [name], [name]
CEO GSO Global Clinical Research B.V.
Medical Writer

SA
10 Apr 2018

94.18

Date

Signature [name]. [name],
University Hospital Hamburg-Eppendorf

1. Purpose of the addendum to SAP

The purpose of this addendum to the Statistical Analysis Plan (SAP) dated 2017Aug25 is to clarify the analysis of the primary endpoint and to add an analysis of the difference between the subgroups.

2. Analysis of the primary endpoint

The primary objective of the clinical trial is to determine the efficacy of Selinexor in combination with standard chemotherapy in patients with relapsed/refractory acute myeloid leukemia (AML) by determination of rate of complete remission (CR) or morphologic complete remission with incomplete blood count recovery (CRi), as defined by the recommendations on diagnosis and management of AML in adults from an international expert panel, on behalf of the European LeukemiaNet.

The primary endpoint is defined as the percentage of patients achieving a CR or CRi. Patients with morphologic leukemia free-state (MLFS) shall be included into the group of responders.

To determine the efficacy of Selinexor in combination with standard chemotherapy, the best response after Selinexor treatment shall be analysed, thus the best response after the induction cycle(s).

A response achieved after stem cell transplantation or in the follow-up period after the patient has received another treatment cannot be used to determine the efficacy of Selinexor in combination with standard chemotherapy as the response may be attributable to the stem cell transplantation or a subsequent therapy.

3. Subsequent updates of the analysis

For the initial analysis of the clinical trial, the best response of each patient throughout the whole study period was used, not the best response obtained after the induction cycle(s).

Therefore, the following tables are required to be updated:

- Frequency tables for best response after Selinexor treatment
- Response rates after Selinexor treatment
- Summary statistics and Kaplan-Meier curves for relapse-free and event-free survival
- Subgroup analyses: Response rates by
 - Primary vs. secondary AML
 - Length of remission: remission < 12 months vs. remission > 12 months
 - Prior SCT: yes vs. no
 - Karyotypic risk group: favourable/intermediate vs. unfavourable vs. unknown karyotypic group

- FTL3 mutation: mutation vs. wildtype
- NPM1 mutation: mutation vs. wildtype

For the updated analysis, the table in attachment 1 shall be used. This table includes

- response data after the induction cycle, updated,
- updated survival data,
- updated data on relapse in the follow-up, and
- updated data on length of remission prior to the SAIL study (for subgroup analysis "length of remission").

Overall survival shall be re-calculated by the current data on survival.

4. Subgroup analysis: Addition of analysis of the difference between the subgroups

Subgroup analysis has currently been conducted separately by subgroup. Additionally, a p-value for the difference between the groups (e.g. patients with early vs. late relapse) shall be provided.

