------------------	---

	
on Monday and Wednesday or on Tuesday and Thursday or on Wednesday and Friday).
 
Treatment will continue until progression of disease (PD) or unacceptable toxicity, withdrawal of consent by the patients, or non-compliance by the patient with protocol requirements.
 
Patients for whom none of the above mentioned is achieved after 2 4-week induction cycles will have their end of treatment and will be followed for overall survival.

Primary Endpoint	Percentage of patients achieving a complete response (CR) or CRI (complete remission without normalization of peripheral blood counts)
Secondary Endpoints	
 • Partial response rate • Percentage of patients undergoing subsequent allogeneic stem cell transplant • Early death rate • Overall survival (OS) • Event-free survival (Events are defined as Death, not achieving a CR or CRI, Relapse after CR or CRI) • Toxicity (acc. to NCI CTC AE v4.03)
Exploratory Endpoints (Optional Studies)	
 • Limited pharmacokinetics to measure plasma concentration of Selinexor • Selinexor-induced changes in mRNA levels of XPO1 and tumor suppressor markers • Selinexor-induced changes in plasma cytokine levels • Selinexor-induced changes in gene expression profiling of leukemic blasts isolated from patients • Expansion of leukemic blasts in mice for therapeutic studies
Efficacy assessment	
Clinical and Bone Marrow Aspirate examinations and safety assessments are performed at baseline, at the End of induction cycles and if applicable at the end of each consolidation cycle. Disease status during maintenance will be evaluated at the end of each cycle and Follow-up after SCT every 3 months ± 28 days
 
If a patient discontinues treatment due to any other reason than disease progression/ death/ withdrawal of informed consent, the disease evaluations shall continue until definition of relapse-free survival are met. This includes patients who wish to discontinue treatment, but agree that further data is captured for the purpose of the study (partial withdrawal).

Safety assessment	All adverse events occurring during the course of the trial and for up to 30 days after the last dose of study medication will be captured, documented and reported. Toxicity will be graded twice weekly during treatment.

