1.1.2.3 Clinical Efficacy

Karyopharm Therapeutics is currently conducting three open label Phase 1 clinical trials to assess the safety, tolerability and efficacy of Selinexor given orally 2-3 times per week. The first study (KCP-330-001) is a dose escalation study in patients with advanced hematological malignancies, the second (KCP-330-002) is a dose escalating study in patients with advanced or metastatic solid tumor malignancies and the third (KCP-330-003), a food effect study, is in patients who have metastatic, locally advanced or locally recurrent soft tissue or bone sarcomas. All patients entering these single-agent phase 1 studies have relapsed after available therapies and have objectively progressing tumors at time of study drug initiation. To date Selinexor has been administered to over 130 patients. The food effect study was initiated in July 2013, so preliminary safety or efficacy data are not yet available.

In the Phase 1 study (KCP-330-001) a total of 39 patients with relapsed AML have been enrolled. As of December 4, of 33 pts who were evaluable for response, complete response (CR) with full hematological recovery was achieved in 4 patients (11%), and CR without hematological recovery (CRi) in 1 patient (3%). Partial Response (PR) was achieved in 2 patients (6%). Morphological leukemia free state was achieved in 1 patient (3%). Ten (29%) of the remaining patients have had stable disease for > 30 days, and 13 (34%) have had progressive disease.

Table 1: Responses in Arm 2 (AML) [16.8 mg/m² to 40 mg/m²] (Study KCP-330-001) as of December 4, 2013

Responses in Arm 2 Acute Myeloid Leukemia Patients as 4-Dec-2013								
Number of Pts Evaluated	Total CRs, CR(i)s, PRs, and SD (%)	CR (%)	CR (i) (%)	PR (%)	MLFS (%)	SD (%)	PD	WC
33	18 (55%)	4 (12%)	1 (3%)	2 (6%)	1 (3%)	10 (30%)	11 (33%)	4 (12%)

Abbreviations: N=number of patients, CR=complete remission, CRi=complete remission without platelet recovery, PR=partial response, MLFS=morphological leukemia free state, SD=stable disease, PD=progressive disease, NE=not evaluable, WC=withdrew consent.

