8 BIOSTATISTICS

8.1 Trial Design and Hypotheses

This is a single-arm trial to evaluate efficacy of Selinexor in patients with relapsed/ refractory AML by complete response rate (CR) or CRi), as defined by the revised recommendations of the International Working Group for diagnosis, standardization of response criteria in Acute Myeloid Leukemia for AML.

The trial tests the null hypothesis that the observed response rate is less or equal than the predefined limit of 30% versus the alternative hypothesis that the response rate is at least 60%.:

$$H_0 : p \leq p_0 \text{ against the alternative hypothesis } H_1 : p \geq p_1.$$

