8.2 Sample Size Calculation

The sample size calculation is based on the evaluation of response rates according to Fleming using the A'Hern (Sample size tables for exact single-stage phase II designs. Statist. Med. 2001;20:859-866.) extension.

In Fleming's procedure two response levels p_0 and p_1 are specified:

- the largest response proportion p_0 which, if true, would clearly imply that the treatment does not warrant further investigations (except for other types of administration, e.g. in standardized combinations); and
- the minimum required response level p_1 that would imply the treatment warrants further investigations.

The following characteristics were specified

- $p_0 = 0.30$
- $p_1 = 0.60$
- $\alpha = 0.05$ (one-tailed) and
- $\beta = 0.10$

$N=25$ patients should participate in the study to ensure a power of $1-\beta=0.90$ for the discrimination of p_0 and p_1 . According to Fleming the null hypothesis should be rejected if at least

$$r = \left\lceil Np_0 + Z_{1-\alpha} \sqrt{Np_0(1-p_0)} \right\rceil + 1$$

responses are observed (x^* denotes the nearest integer to). With p_0 and N defined as above and $Z_{1-\alpha} = (1 - \alpha)$ -quantile of the normal distribution = 1.645 at least 12 responders should be observed to show the efficacy as postulated.

Using the same approach in the 15 additional patients, submitted to an adapted drug regimen, the power will be 80% to discriminate a $p_0=30\%$ (expected CR rate) from a $p_1=65\%$ (meaningful increase in CR rate), if 8 out of 14 completed patients are considered as responders, with a one-tailed alpha error of 5%.

Alternatively, the power will be 90% to discriminate a $p_0=30\%$ from a $p_1=70\%$ again if 8 out of 14 completed patients are considered as responders, with a one-tailed alpha error of 5%.

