17.6 Appendix 6 – NCI-CTCAE version 4.03

17.7 Appendix 7- Response criteria in AML

Definitions of response criteria are based primarily on those given by Döhner et al.⁽¹⁾

Response criteria	Absolute Neutrophil count	Absolute Platelets count	Bone marrow Blasts (%)	Comments
Complete remission (CR)*	$>1.0 \times 10^9/L$ (1000/ μ L)	$>100 \times 10^9/L$ (100.000/ μ L)	<5	Absence of blasts with Auer rods; Absence of EMD; independence of red cell transfusion
CR with incomplete recovery (CRi) [†]	$<1.0 \times 10^9/L$ (1000/ μ L)	$<100 \times 10^9/L$ (100.000/ μ L)	<5	All CR criteria except for residual neutropenia or thrombocytopenia.
Morphologic leukemia-free state [‡]	NA	NA	<5	Absence of blasts with Auer rods; Absence of EMD; no hematologic recovery required
Partial remission (PR)	$>1.0 \times 10^9/L$ (1000/ μ L)	$>100 \times 10^9/L$ (100.000/ μ L)	5 to 25	Relevant in the setting of phase 1 and 2 clinical trials only; decrease of pretreatment bone marrow blast percentage by at least 50%
Cytogenetic CR (CRc) [§]	$>1.0 \times 10^9/L$ (1000/ μ L) or $<1.0 \times 10^9/L$ (1000/ μ L)	$>100 \times 10^9/L$ (100.000/ μ L) or $<100 \times 10^9/L$ (100.000/ μ L)	<5	Reversion to a normal karyotype at the time of morphologic CR (or CRi) in cases with an abnormal karyotype at the time of diagnosis; based on the evaluation of 20 metaphase cells from bone marrow
Molecular CR (CRm) ⁱ	No standard definition; depends on molecular target			

Treatment failure	
Resistant disease (RD)	Failure to achieve CR or CRi (general practice; phase 2/3 trials); or failure to achieve CR, CRi, or PR (phase 1 trials); only includes patients surviving ≥ 7 days following completion of initial treatment, with evidence of persistent leukemia by blood and/or bone marrow examination

Death in aplasia	Deaths occurring \geq 7 days following completion of initial treatment while cytopenic; with an aplastic or hypoplastic bone marrow obtained within 7 days of death, without evidence of persistent leukemia
Death from indeterminate cause	Deaths occurring before completion of therapy; or < 7 days following its completion; or deaths occurring ≥ 7 days following completion of initial therapy with no blasts in the blood, but no bone marrow examination available
Relapse [¶]	Bone marrow blasts $\geq 5\%$; or reappearance of blasts in the blood; or development of extramedullary disease

EMD extamedullary disease

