The sample size calculation ended up in 25 patients to be recruited to ensure a power of 90 % for the discrimination of p_0 and p_1 . In addition, 15 additional patients were submitted to an adapted drug regimen (flat dose 60mg of Selinexor instead of 40 mg /m² of Selinexor). Using a similar approach, the power will be 80 % to discriminate a $p_0=30$ % from a $p_1=65$ %, with a one-tailed α of 0.05 %.

6 Statistical hypotheses

The purpose of this study is to evaluate efficacy of Selinexor in patients with relapsed/ refractory AML by complete response rate (CR or CRi). The null-hypothesis to be tested is

H_0 : *The observed response rate is less or equal than 30 %*

against the alternative hypothesis

H_1 : *The observed response rate is over 30 %*

7 Analysis sets

A detailed subject classification document will be prepared in a Data Review meeting prior database lock. The document will assign patients to the respective analysis sets depending on the observed protocol violations.

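### The SAP addendum, written after an initial analysis, counts MLFS as response without a reason and leaves the CR/CRi null of 30% and its decision rules as they were

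*SAP*

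**What the plan says.** **Endpoint.** The protocol synopsis gives the primary endpoint as "Percentage of patients achieving a complete response (CR) or CRI (complete remission without normalization of peripheral blood counts"). Protocol 2.1 and 8.1, SAP sections 2 and 6, and the titles of SAP Tables 14.2.1.3 and 14.2.1.4 also name CR or CRi.

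**Benchmark.** Protocol 8.1: "The trial tests the null hypothesis that the observed response rate is less or equal than the predefined limit of 30" per cent. SAP section 6 has the same null: "The observed response rate is less or equal than 30" per cent. For the first 25 patients, Protocol 8.2 requires that "at least 12 responders should be observed to show the efficacy as postulated". For the 15 additional patients it gives the power "if 8 out of 14 completed patients are considered as responders, with a one-tailed alpha error of 5" per cent.

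**MLFS.** Protocol Appendix 7 gives MLFS its own row: "Absence of blasts with Auer rods; Absence of EMD; no hematologic recovery required". A footnote places its use in phase 1 trials. For phase 2/3 trials the same appendix defines resistant disease as not reaching CR or CRi.

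**Addendum.** Version 1, 4 April 2018, describes its purpose as clarifying the primary analysis. Section 2 repeats CR or CRi as the endpoint, and the next sentence reads: "Patients with morphologic leukemia free-state (MLFS) shall be included into the group of responders". Section 2 also limits response to the best response after the induction cycle(s), because a later response could be due to transplantation or another therapy. Section 3 says the initial analysis used best response over the whole study, and lists the tables to be redone from a patient-level table dated 27 March 2018.

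**The concern.** The addendum's definition of the endpoint and its group of responders disagree in consecutive sentences. Its only stated rationale concerns the time window for response. Nothing explains why MLFS counts.

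The 30% limit was chosen for CR or CR/CRi; Protocol 8.2 labels it the expected CR rate. A wider numerator set against an unchanged limit is a different and easier test. By Protocol 8.4.1 the responder rate is the only analysis that is not purely descriptive, so this affects the one confirmatory result.

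The trial is open-label, and the sentence was written after response data had been analysed. That does not show motive. It does mean that a favourable result could be attributed to the late definition, and the documents contain no reason with which to answer.

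There is also a conflict with event-free survival. Protocol 2.2 and SAP section 2 count failure to reach CR or CRi as an event, so under those definitions an MLFS patient is a primary responder and an EFS failure.

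**Working it through.** **Inputs from Protocol 8.2:** p0 = 0.30; p1 = 0.60 (n = 25, 90% power); p1 = 0.65 (80%) or 0.70 (90%) for n = 14; one-sided alpha 0.05; success at r = 12 of 25 and r = 8 of 14.

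**Step 1. Reproduce the design.**

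Fleming cutoff: nearest integer to n·p0 + 1.645·√(n·p0·(1−p0)), plus 1.
- n = 25: 7.5 + 1.645·√5.25 = 11.27, nearest integer 11, r = 12.
- n = 14: 4.2 + 1.645·√2.94 = 7.02, nearest integer 7, r = 8.

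Exact operating characteristics, P(X ≥ r) = Σ(k = r to n) C(n,k)·p^k·(1−p)^(n−k):
- 12/25: alpha 4.42%, power 92.2% at 0.60.
- 8/14: alpha 3.15%, power 81.6% at 0.65 and 90.7% at 0.70.

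The protocol's rules reproduce.

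**Step 2. A pooled cutoff.** The SAP also analyses all patients together and states no pooled rule. Its planned statistic is the rate with a Wilson 95% interval. The smallest count of 40 whose lower limit exceeds 30% is 18 (17/40 gives 28.5%, 18/40 gives 30.7%). I use 18/40 as a derived cutoff. The same criterion gives 12/25 (lower limit 30.03%) and 8/14 (32.6%), which matches the protocol's rules.

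**Step 3. Count MLFS and keep the rules.** Let d be the percentage points of patients who are MLFS but not already CRi. With true CR/CRi at exactly 30%, the counted rate is p = 0.30 + d/100. The documents do not give d for this regimen, so the values below are assumptions.

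| d (points) | p | P(≥12 of 25) | P(≥8 of 14) | P(≥18 of 40) |
|---|---|---|---|---|
| 0 | 0.30 | 4.4% | 3.15% | 3.2% |
| 3 | 0.33 | 8.6% | 5.45% | 7.6% |
| 5 | 0.35 | 12.5% | 7.5% | 12.4% |
| 10 | 0.40 | 26.8% | 15.0% | 31.1% |

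At d = 1 the 12/25 rule is already at 5.6%. The 8/14 rule passes 5% between d = 2 (4.6%) and d = 3.

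**Step 4. Cutoffs that would hold alpha at 5% or less with MLFS counted.**
- Null 33%: 13/25 (alpha 3.8%) and 9/14 (1.6%). Power at the unchanged alternatives of 0.60 and 0.65 is 84.6% and 64.1%.
- Null 40%: 15/25 (3.4%) and 10/14 (1.8%).

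**Step 5. What the documents say about the MLFS rate.** The only figure is in Protocol 1.1.2.3: 1 of 33 AML patients on single-agent selinexor. The exact (Clopper-Pearson) 95% interval is 0.1% to 15.8%. It describes a different treatment, and it measures MLFS frequency rather than d.

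**The case against.** The strongest reply is that the sentence may change little.

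- **Overlap with CRi.** In Appendix 7 both categories need fewer than 5% marrow blasts. A patient with MLFS and both cytopenias can also meet CRi unless dependent on red cell transfusion. On that reading the addendum does clarify, and d could be near zero. This stands as a limit on the size. It does not remove the contradiction: Appendix 7 gives MLFS its own row, and if every MLFS patient were already CRi the sentence would not be needed.
- **The initial analysis may already have counted MLFS.** Addendum section 3 names only the response window as the difference from that analysis. This stands. What is established is that the written definition changed late; whether any patient's status changed is unknown.
- **Other changes affect the rate too.** The post-induction restriction can only lower it, and the updated response data could move it either way. This also stands, so no net bias can be claimed. But the changes are separable, and a justified restriction does not justify an unexplained widening.
- **The 12/25 and 8/14 rules appear only in the protocol.** True: unchanged here means that the addendum is silent. The SAP keeps the 30% null and one-sided alpha in its sections 5 and 6, and its Wilson interval read against 30% gives the same counts, so the mismatch remains.
- **The larger figures need d = 10.** Correct. At d = 3 the 8/14 rule is only just above 5%.

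**Conclusion.** The concern holds: the plan is wrong as written and must be corrected. Followed literally, it sets a CR+CRi+MLFS rate against a limit chosen for CR/CRi, under a definition introduced without a reason after an initial analysis.

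The size depends on d. For d from 0 to 10 points, the false-positive rate with respect to CR/CRi runs from 4.4% to 26.8% (12/25), from 3.15% to 15.0% (8/14), and from 3.2% to 31.1% for all 40 patients on the derived 18/40 cutoff. These figures assume true CR/CRi of exactly 30%, independent patients and unchanged cutoffs, and they isolate the MLFS sentence from the addendum's other changes. The net effect of the whole addendum on the reported rate cannot be determined from the documents.

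**What to change.** Issue a dated revision of the addendum that replaces the MLFS sentence with:

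> Primary responders are patients with CR or CRi as best response after the induction cycle(s).

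Then:
- Keep the post-induction restriction; it has a stated reason.
- Show MLFS as its own row in the best-response table, and count it as non-response in the comparison with 30% and in the response subgroup tables.
- State how a patient who meets both the CRi and MLFS rows of Appendix 7 is classified, so that the boundary is not settled case by case.
- Report CR+CRi+MLFS only as a sensitivity analysis labelled post hoc.
- State in the study report that an initial analysis preceded the addendum, whether it counted MLFS, and both results.

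The cost is a short revision, one extra table row and a disclosure. The headline response rate may be slightly lower. No data are lost.
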